5.4.5 ECG Data

5.4.5.1 ECG analyses

Actual values of numeric ECG parameters will be summarized by visit. number of evaluable subjects, mean, standard deviation, 25% and 75% quartiles, min and max values will be presented at each visit for placebo-controlled and LTE period active treatment period. Similarly change from baseline values will be summarized in the same fashion for placebo-controlled and LTE active treatment period.

Summary of ECGs (number of normal, <abnormal, not adverse event>, or <abnormal, adverse event>) at scheduled visits will be presented by the LTE treatment group through the placebo-controlled and LTE active treatment period.

CONFIDENTIAL

The information contained herein may not be used, disclosed, or published without the written consent of Biogen MA Inc.

	Statistical Analysis Plan Long-Term Extension Period	V1.0
---	---	-------------

Shift table from normal or unknown ECG at baseline to ever abnormal ((<abnormal, not adverse event>, or <abnormal, adverse event>) post-baseline ECG will be summarized for the placebo-controlled and LTE active treatment group. The worst post-baseline record of each subject is selected.

For the above mentioned ECG analyses, for early start subjects, the placebo-controlled baseline will be used while for late start subjects, the LTE baseline will be used.

In addition, PR and QTcF values will be summarized. Please see the detail in the SAP for placebo-controlled period.

Visit windows for by visit summaries

For ECG data that are summarized by visit, assessment from all scheduled visits, EOT visit, EOS visit and unscheduled visits will be mapped to an appropriate analysis visit using a windowing scheme ([Appendix I](#)).

5.4.6 Vital Sign Data

5.4.6.1 Vital Sign Data Analyses

Vital sign parameters include temperature, diastolic blood pressure, systolic blood pressure, heart rate, and respiration rate. The descriptive statistics for actual values will be summarized by all the visits in the combined placebo-controlled and LTE active treatment period. The lines of mean vital sign over time by LTE treatment group will be graphed in the combined placebo-controlled and LTE active treatment period.

Summary of change from baseline including number of subjects, mean, standard deviation, median, minimum, and maximum values will be summarized in the placebo-controlled and LTE active treatment period. Placebo-controlled baseline will be used for early start subjects and LTE baseline will be used for late start analysis.

A by-patient listing for all vital sign parameters in the combined placebo-controlled and LTE period will also be presented.

The analysis of vital signs will also focus on the incidence of clinically relevant outliers.

For details of criteria to assess potential clinically relevant outliers in vital sign, refer to section 5.4.6 in the SAP for the placebo-controlled period. The number of clinically relevant outliers determined by each criterion will be summarized across combined placebo-controlled and LTE active treatment period by treatment group.

Visit windows for by visit summaries

For vital sign data that are summarized by visit, assessment from all scheduled visits, EOT visit, EOS visit and unscheduled visits will be mapped to an appropriate analysis visit using a windowing scheme ([Appendix I](#)).

CONFIDENTIAL

The information contained herein may not be used, disclosed, or published without the written consent of Biogen MA Inc.

	Statistical Analysis Plan Long-Term Extension Period	V1.0
---	--	-------------

5.4.7 Physical Examination

Clinically significant findings during physical examinations will be recorded as AEs. Abnormal findings from physical examination will be included in AE listing..

5.4.8 Neurological Examination

Clinically significant findings during neurological examinations will be recorded as AEs. Abnormal findings from neurological examination will be included in AE listing..

5.4.9 Safety MRI Data

The following MRI data will be summarized by LTE treatment group using safety MRI population for placebo-controlled and LTE active treatment period:

- Number of subjects with new or worsening of vasogenic edema (VE) at post-baseline
 - New VE or questionable VE is considered as subjects who has a VE which is worsening as post-baseline or for the following:
 - The subject has answered “Not-Applicable” at any post-baseline visit for question: VE on this MRI as compared to previous MRI
 - The subject has answered “VE present and increased in size” at any post-baseline visit for question: VE on this MRI as compared to previous MRI
 - Worsening of VE from baseline is defined as any severity increase compared to baseline. The following sequence indicates the increase of the severity:
 No VE present < Questionable presence of VE (Mild Severity) < Questionable presence of VE (Moderate Severity) < Questionable presence of VE (Severe Severity) < VE present (Mild Severity) < VE present (Moderate Severity) < VE present (Severe Severity)
- Number of subjects with new microhemorrhages (mH) findings at post-baseline
 - New mH is define as subjects who has mH increased in number and/or size at any post-baseline comparing to the baseline. If a subject has no mHs at baseline, then new mH is defined as any initial identification at any post-baseline visit.
- Number of subjects with macrohemorrhages (MA) (>1cm) at post-baseline
- Number of subjects with new superficial siderosis (SS) (>1cm³) at post-baseline
- Number of subjects with new SS (≤1cm³) at post-baseline

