3.2 Analyses Period

Depending on the purpose, different analyses will be conducted on the following study periods:

1. LTE period. Only data in the LTE period will be included in these analyses. This LTE analysis period will be applied to all the AE analyses, and the analyses will include all subjects who were dosed in the LTE period.
2. Placebo-controlled and LTE period. All the data in the placebo-controlled and LTE periods will be included in these analyses. This analysis period will be applied to analyses including, but not limited to all efficacy analyses and listings. The analyses will include all subjects who were dosed in the study including those who did not enroll into the LTE period. For example, line plot of CDR sum of box mean change from baseline over time. in the placebo-controlled and LTE period.
3. Placebo-controlled and LTE active treatment period. Active treatment period is defined as the study period(s) that a subject received BIIB092. For early start subjects – subjects who received BIIB092 in both placebo-controlled and LTE period, all the data (placebo-controlled and LTE periods) will be included in the analyses. For late start subjects – subjects who received placebo in the Placebo-controlled period and BIIB092 in the LTE period, only data in the LTE period will be included. This analysis period will be applied to majority of safety tables, and the analyses will include all subjects who were dosed in the study except for subjects who received only placebo in the placebo-controlled period and did not get dosed in the LTE period. An example is the incidence rate of adverse events in the placebo-controlled and LTE active treatment period.

Subjects to be included in a certain output is determined by both the analysis set and the analysis period. For example, the incidence table of adverse events in the LTE period will include subjects in the safety population for the LTE period, i.e., all randomized subjects who received at least one dose of study treatment in the LTE period. The incidence rate table of adverse events in the placebo-controlled and LTE active treatment period will include subjects in the safety population for the active treatment period, i.e., all randomized subjects who received at least one dose of study treatment in the active treatment period. In this SAP we do not separately define the analysis set in each analysis period.

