5.4.2.2 Incidence Rate Analysis

Incidence rate of AEs based on the entire follow-up time for subjects with at least 1 AE in LTE period may be summarized by system organ class and preferred terms. The incidence rate tables will be presented by LTE treatment group. The entire follow-up time for LTE period is from the first dose in LTE period until the last day on study.

Follow-up adjusted incidence rate of AEs may also be summarized for placebo-controlled and LTE active treatment period, due to the different length of placebo-controlled and LTE active treatment period in early start versus late start high-dose BIIB002 subjects. The entire follow-up time is from the first dose in active treatment period (placebo-controlled period first dose of BIIB092 for early start subjects and LTE period first dose of BIIB092 for late start subjects) until the last day in the study.

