5.4.3.2 Qualitative analyses

For qualitative analyses, all values will be included (not just the “analyzed record” within each visit window in the quantitative analyses).

Shift analyses

Laboratory data will be summarized using shift tables where appropriate for the placebo-controlled and LTE active treatment period. Each subject’s hematology, blood chemistry and urinalysis values will be flagged as “low”, “normal”, or “high” relative to the normal ranges of the central laboratory or as “unknown” if no result is available.

For each parameter, the analysis will be based on subjects with at least one post-baseline value. Shifts from baseline to high/low status will be presented for hematology, blood chemistry coagulation, serology, and urinalysis. Shift to low includes normal to low, high to low, and unknown to low; Shift to high includes normal to high, low to high, and unknown to high. Subjects need to have at least one post-baseline evaluation and a baseline value not low or high (including missing) in order to be included in the analysis for corresponding categories in the analyses.

For early start subjects, the placebo-controlled baseline will be used and shifts that occurred in either placebo-controlled or LTE period will be included. For late start subjects, the LTE baseline will be used and shifts that occurred in the LTE period based on LTE baseline will be included.

Potentially Clinically Significant laboratory abnormalities analyses

Please refer to the placebo-controlled SAP for the parameters and criteria for potentially clinically significant laboratory abnormalities analyses.

The number of subjects with potentially clinically significant laboratory abnormalities post-baseline will be summarized for the placebo-controlled and LTE active treatment period.

Subjects need to have at least one post-baseline evaluation in the active treatment period and a baseline value not potentially clinically significant (including missing) in order to be included in the analysis.

Same as the shift analysis, for early start subjects, the placebo-controlled baseline will be used and abnormalities that occurred in either placebo-controlled or LTE period will be included. For late start subjects, the LTE baseline will be used and PCS abnormalities that occurred in the LTE period based on LTE baseline will be included.

CONFIDENTIAL

The information contained herein may not be used, disclosed, or published without the written consent of Biogen MA Inc.

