5.4.4 C-SSRS Data

Suicidal ideation events include 11 categories: (1) Wish To Be Dead, (2) Non-Specific Active Thoughts, (3) Active Thoughts Without Intent To Act, (4) Active Thoughts With Some Intent—No Plan, (5) Active Thoughts with Plan and Intent. Suicidal behavior events include: (6) Preparatory acts or behavior, (7) Aborted Attempt, (8) Interrupted Attempt, (9) Actual Attempt, (10) Suicidal behavior, (11) Completed Suicide. Another “Yes/No” question of whether the subject has engaged in non-suicidal self-injurious behavior is also collected.

The analysis will be based on the safety population. Number of subjects in each ideation category at any post-baseline visit, number of subjects in each suicidal behavior category at any post-baseline visit, number of subjects with at least one suicidal ideation or behavior event at any post-baseline visit, and subjects who have engaged in non-suicidal self-injurious behavior at any post-baseline visit will be summarized in the placebo-controlled and LTE active treatment period. A listing of C-SSRS data by subjects will be provided.

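### Counts of safety MRI, laboratory, C-SSRS and vital-sign findings are not adjusted for an active-treatment period 80 weeks longer in the early-start groups, so contrasts with late-start 2000 mg are biased

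*SAP*

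**What the plan says.** SAP 3.2 defines the placebo-controlled and LTE active treatment period differently by group. For early-start subjects, "all the data (placebo-controlled and LTE periods) will be included in the analyses". For late-start subjects the rule is: "subjects who received placebo in the Placebo-controlled period and BIIB092 in the LTE period, only data in the LTE period will be included". The SAP applies this period to most safety tables.

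Four sections then plan counts over it:

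- **Safety MRI (5.4.9):** "The following MRI data will be summarized by LTE treatment group using safety MRI population for placebo-controlled and LTE active treatment period". The items listed are numbers of subjects with new or worsening edema, new microhemorrhage, macrohemorrhage and new siderosis.
- **Laboratory (5.4.3.2):** shifts from baseline, and "The number of subjects with potentially clinically significant laboratory abnormalities post-baseline will be summarized for the placebo-controlled and LTE active treatment period".
- **C-SSRS (5.4.4):** "Number of subjects in each ideation category at any post-baseline visit", with similar counts for behavior and self-injury.
- **Vital signs (5.4.6.1):** "The number of clinically relevant outliers determined by each criterion will be summarized across combined placebo-controlled and LTE active treatment period by treatment group". This wording counts outliers and does not say subjects.

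None of these sections adds a rate per subject-year, a count limited to equal time on drug, or a caution about unequal follow-up. For adverse events the SAP does more. Section 5.4.2.1 plans tables for the LTE period, for which 3.2 says "Only data in the LTE period will be included", and marks selected tables for incidence rates over the active period. Section 5.4.2.2 says follow-up-adjusted rates may be given, "due to the different length of placebo-controlled and LTE active treatment period in early start versus late start" subjects.

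**The concern.** A count of subjects who ever had a finding rises with the length of observation and the number of assessments. If the columns of one table cover different lengths, the longer-observed columns show more findings even when the underlying risk is the same. Here every early-start column, including 125 mg, would look worse than late-start 2000 mg at equal risk. A true excess in newly exposed late-start subjects could be hidden for the same reason.

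The late-start group matters in its own right. The Version 4 amendment rationale in the protocol singles out the Week 104 MRI as a key safety check for participants switching from placebo. Adverse-event tables do not fully cover the gap. Under protocol 15.1.1, an abnormal laboratory, vital-sign or ECG result is an adverse event only if it is serious, needs corrective therapy or is judged clinically significant.

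**Working it through.** **1. The offset.** Protocol Table 2 puts Week 80 at Day 561: (561 − 1)/7 = 80 weeks. The safety MRI target days in SAP Appendix I, Tables 15 and 16, agree: 729 − 169 = 1093 − 533 = 1583 − 1023 = 560 days = 80 weeks.

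**2. Observation time.** For subjects who spend L weeks in the LTE, the early/late ratio is (80 + L)/L.

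| LTE ends at | L (weeks) | Ratio |
|---|---|---|
| Week 104 | 24 | 104/24 = 4.33 |
| Week 128 | 48 | 128/48 = 2.67 |
| Week 156 | 76 | 156/76 = 2.05 |
| Week 226 | 146 | 226/146 = 1.55 |
| Week 238 | 158 | 238/158 = 1.51 |

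**3. Proportion ever positive at equal risk.** The documents give no event rates for these findings, so a constant hazard h is assumed and varied. P = 1 − exp(−h × weeks/52.18). At h = 0.05 and Week 226: 1 − exp(−0.05 × 4.33) = 19.5% against 1 − exp(−0.05 × 2.80) = 13.1%. At Week 104: 1 − exp(−0.05 × 1.99) = 9.5% against 1 − exp(−0.05 × 0.46) = 2.3%.

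| h per 100 subject-years | To Week 226, early vs late (ratio) | To Week 104, early vs late (ratio) |
|---|---|---|
| 1 | 4.2% vs 2.8% (1.54) | 2.0% vs 0.5% (4.30) |
| 5 | 19.5% vs 13.1% (1.49) | 9.5% vs 2.3% (4.17) |
| 10 | 35.2% vs 24.4% (1.44) | 18.1% vs 4.5% (4.02) |
| 20 | 57.9% vs 42.9% (1.35) | 32.9% vs 8.8% (3.74) |
| 50 | 88.5% vs 75.3% (1.18) | 63.1% vs 20.5% (3.07) |

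**4. Scheduled post-baseline assessments**, counted from the Appendix I visit tables for subjects who enter the LTE:

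| Domain | Full plan, early vs late | Through Week 104 |
|---|---|---|
| Safety MRI | 6 vs 3 | 4 vs 1 |
| C-SSRS | 9 vs 6 | 4 vs 1 |
| Laboratory | 13 vs 8 | 6 vs 1 |
| Vital-sign visits | 59 vs 38 | 27 vs 6 |

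**5. Why Week 104 is shown.** SAP 5.6.2 says no subject reached Week 226. The top infusion class in SAP 5.2.4 is 21–26. Protocol 11.1.1 gives 20 infusions in the placebo-controlled period, so 26 leaves six in the LTE, the sixth at Week 100. This is an inference about when dosing stopped.

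**6. Early-start subjects who never enter the LTE** stay in the table and shorten mean follow-up. If 20% do so (assumed) with 40 to 90 weeks each, the time ratio at L = 24 is (0.8 × 104 + 0.2 × 40)/24 = 3.8 to (0.8 × 104 + 0.2 × 90)/24 = 4.2.

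**7. After adjustment.** With time censored at the first occurrence, a constant hazard of 5 gives 5.0 against 5.0 per 100 subject-years. SAP 5.4.1.3 instead divides subjects with an event by their entire follow-up. That is close for rare findings (9.5%/1.99 = 4.8 vs 2.3%/0.46 = 4.9, from unrounded values) but not for common ones: at h = 50, 63.1%/1.99 = 31.7 vs 20.5%/0.46 = 44.6.

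**The case against.** The plan is better than a quick reading suggests.

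A reader might infer that no planned safety table compares the groups over like time. The documents do not support that. Laboratory values (5.4.3.1) and vital signs (5.4.6.1) are summarized by visit, and for late-start subjects change is measured from the LTE baseline. ECG normal/abnormal status is tabulated at scheduled visits (5.4.5.1). Appendix I also defines LTE-baseline windows for C-SSRS and MRI, although 5.4.4 and 5.4.9 name no by-visit table. These displays lessen the problem, but means by visit do not show how many subjects had a finding per unit of time.

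A reader might also infer that the primary LTE endpoint is compromised. It is not: that endpoint is the incidence of AEs and SAEs, which have LTE-period tables and rates.

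The size is open to challenge too. A hazard concentrated soon after first exposure would bring the ratio nearer 1. The displays are descriptive with no tests, and exposure is tabulated by group, so a careful reader could discount the counts. These points limit the consequence. They do not justify adjusting AEs while leaving these four domains unadjusted.

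The separate placebo-controlled SAP was not available. The LTE SAP refers to it for definitions and criteria in these areas, not for an exposure adjustment.

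**Conclusion.** The concern holds for safety MRI, laboratory shifts and potentially clinically significant values, C-SSRS and vital-sign outliers, and only for contrasts of an early-start group with late-start 2000 mg. The 125 mg, 375 mg, 600 mg and early-start 2000 mg groups share one period definition, so comparisons among them are free of this offset.

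At an equal constant hazard, and for findings that are not frequent, the early-start proportion is inflated about 1.5-fold if the LTE ran to plan and about 4-fold if it ended near Week 104. The larger figure should not be read as established. The SAP gives no safety cut-off at Week 104, where its explicit limit is for the interim efficacy analysis, and its weeks-on-treatment classes are open-ended at 96 weeks or more. The ratios also assume full follow-up, and they shrink as findings become common.

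**What to change.** In SAP 5.4.9, 5.4.3.2, 5.4.4 and 5.4.6.1, and optionally for the ever-abnormal ECG shift in 5.4.5.1, keep the planned counts and add:

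- **A rate:** subjects with a first occurrence per 100 subject-years, with time from first BIIB092 dose to that occurrence or the last relevant assessment. This adapts 5.4.1.3 by stopping the clock at the first occurrence, for the reason in step 7. For vital signs, state that the numerator is subjects.
- **An equal-time count:** subjects with a finding over the same time since first BIIB092 dose in all five groups, with the number of assessments shown. Schedules do not align exactly. The first post-baseline MRI is at Week 28 for early start and at Week 104, 24 weeks after first dose, for late start.

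If an LTE-period table from the LTE baseline is also shown, label it as comparing previously exposed with newly exposed subjects. It equalizes observation time but not prior exposure, and it absorbs earlier findings into the early-start baseline.

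The cost is SAP wording and a few extra tables from data already collected, with no new visits or assessments.

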5.4.10 COVID-19 Related Safety Analysis

All AE tables due to COVID-19 will be summarized for LTE period and PC and LTE active treatment period. Please refer to the placebo-controlled SAP for more details.

CONFIDENTIAL

The information contained herein may not be used, disclosed, or published without the written consent of Biogen MA Inc.

	Statistical Analysis Plan Long-Term Extension Period	V1.0
---	--	-------------

5.5 Pharmacokinetics Analysis

The Serum PK evaluable set as defined in [Section 3.1](#), will be used for the description of the serum concentration data, and for the estimation of serum PK parameters. The CSF PK evaluable set as defined in [Section 3.1](#), will be used for the description of CSF concentration data. PK analysis will be conducted with serum and CSF concentrations of BIIB092 by visit and dose group. Subjects who receive BIIB092 125mg once every 4 weeks will be analyzed separately from those who receive 375mg once every 12 weeks. The summaries and listing will be done using the combined placebo-controlled and LTE active treatment period.

Atypical drug concentrations (e.g., very low or very high) will be excluded from the analysis, if no apparent explanation exists. Concentration observations will also be removed from the data set if

- i) corresponding dosing or sampling times are missing or cannot be reconstructed
- ii) large deviations between actual administered dose and nominal dose exists
- iii) large deviations between scheduled and actual sampling days or times exists
- iv) large deviations between actual and nominal dose administration time exists.

All deletions of data points will be appropriately documented.

5.5.1 Serum and CSF PK Concentration Profile

Individual serum and CSF concentrations will be listed for BIIB092. Concentrations below the lower limit of quantification (LLOQ) will be indicated by “BLQ”. Differences between scheduled and actual sampling times will be listed for these subjects, along with the percentage differences between nominal and actual dose amount. Additional listings may be generated as deemed necessary.

Descriptive statistics (N, arithmetic mean, standard deviation, geometric mean, CV, median, minimum, and maximum), will also be used to summarize serum PK and CSF concentrations of BIIB092 by visit/scheduled time points and dose group. For the purpose of calculating typical descriptive statistics (n, mean, SD, %CV, geometric mean, geometric %CV, median, minimum, and maximum) for serum PK, BLQ value on pre-day 1 of study treatment will be set to 0, and all post first dose of study treatment BLQ values will be set to half the LLOQ value. In linear and semi- plots, all BLQ values will be treated as LLOQ/2. Mean CSF concentrations that are BLQ will be presented as BLQ, and the SD and %CV will be reported as not applicable. When summarizing concentrations or PK parameters in serum and CSF, a minimum of 2 values are required to show the arithmetic mean and geometric mean, and at least 3 values are required to show the standard deviation and coefficient of variation (CV).

Serum and CSF concentrations of BIIB092 will be plotted versus time by dose group on both a linear and a logarithmic scale. Additional plots may be included as deemed necessary.

CSF to serum concentration ratio will be computed using pre-infusion concentrations at week 12, 48, 76, 128, 176, and 224. Individual ratios along with descriptive statistics (N, arithmetic mean, standard deviation, geometric mean, CV, median, minimum, and maximum) at 12, 48, 76, 128,

CONFIDENTIAL

The information contained herein may not be used, disclosed, or published without the written consent of Biogen MA Inc.

176, and 224 weeks, by dose will be listed. Any BLQ value will be excluded from CSF to serum ratio calculation, and exclusions will be appropriately documented. Individual CSF vs. serum concentrations above LLOQ (for both serum and CSF) will be plotted (scatter plot) by week, color coded by dose.

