4.5. Overall Benefits and Risks Assessment

4.5.1. Overall Benefit

BIIB092 has the potential to slow or stop the spread of tau pathology observed in neurodegenerative diseases such as PSP, AD, and other tauopathies.

In participants with PSP, BIIB092 has been evaluated in 2 completed clinical studies (Studies CN002001 and CN002003) and is currently being evaluated in the ongoing Studies 251PP201 and 251PP301. The first-in-human study of BIIB092 (Study CN002001) was designed as a randomized, double-blind, placebo-controlled, SAD study in healthy participants to characterize the safety, tolerability, PK, PD, and immunogenicity of single doses of BIIB092, ranging from 21 to 4200 mg. Study CN002003, a Phase 1b study, was designed as a randomized, double-blind, placebo-controlled MAD study to characterize the safety, tolerability, PK, PD, and immunogenicity of multiple doses of BIIB092, ranging from 150 to 2100 mg, in participants with PSP. In both of these completed studies, BIIB092 was found to be well tolerated at the doses tested in both healthy participants and participants with PSP. The ongoing Phase 1b study, Study 251PP201, is designed as an open-label extension study to evaluate the long-term safety and tolerability of multiple doses of BIIB092 in participants with PSP who participated in Study CN002003. Several interim analyses of the data being collected in this study have been performed to date. Study 251PP301 is an ongoing Phase 2b study designed as a randomized, double-blind, placebo-controlled, parallel-group study to evaluate the efficacy and safety of IV-administered BIIB092 in participants with PSP.

In participants with AD, this study (Study 251AD201) will evaluate the safety and efficacy of BIIB092.

Based on the PK and PD data from Studies CN002001 and CN002003, the mean concentrations of BIIB092 in CSF increased in a generally dose-proportional manner. A robust and persistent lowering of unbound N-terminal tau was observed following administration of single and multiple doses of BIIB092 in healthy participants and in participants with PSP, consistent with the observations in cynomolgus monkeys.

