3.1 Analysis Sets

- **Full Analysis Set (FAS):**
The FAS includes all randomized subjects who received at least one dose of study treatment (BIIB092 or placebo). In analyses performed on the FAS, subjects will be analyzed, based on the intention-to-treat principle, according to their randomized treatment assignment regardless of treatment received.
- **Safety Analysis Set:**
The safety Analysis Set includes all randomized subjects who received at least one dose of study treatment (BIIB092 or placebo), essentially the same set of participants included in the FAS. In analyses performed on the Safety Analysis Set, subjects will be analyzed according to their actual treatment received.
- **Safety MRI Evaluable Set:**
The Safety MRI Evaluable Set is defined as subjects in the FAS who had at least one post-baseline safety MRI scan.
- **Serum PK Evaluable Set:**
The serum PK evaluable set is defined as subjects in the FAS who had at least one measurable post-baseline BIIB092 concentration in serum before the End of Study of LTE.
- **CSF PK Evaluable Set:**
The CSF PK evaluable set is defined as subjects in the FAS who had at least one measurable post-baseline BIIB092 concentration in CSF.
- **CSF PD Evaluable Set:**
The CSF PD evaluable set is defined as subjects in the FAS who had lumbar puncture (LP), which will be used in analyses, such as subject accounting and summary of AE related to LP. The CSF PD Modified Evaluable Set is defined as subjects in the FAS who have baseline and at least one post baseline assessment of the specific parameter being analyzed in CSF.
- **Tau PET Evaluable Set**
The tau PET evaluable set is defined as subjects in the FAS who had tau PET, which will be used in analyses, such as subject accounting and summary of AE related to tau PET. The tau PET Modified Evaluable Set is defined as subjects in the FAS who had a valid baseline and a post-baseline tau PET SUVR measure using the 18F-MK6240 tracer.

	Statistical Analysis Plan Long-Term Extension Period	V1.0
---	---	-------------

- Anti-drug antibody (ADA) Evaluable Set:
The evaluable set for anti-drug antibody is defined as subjects in the FAS who have an evaluable post-baseline ADA sample.

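### Excluding BLQ values from the CSF-to-serum BIIB092 ratio can bias the by-dose ratio upward, chiefly in the low-dose regimens, by an amount the documents do not let us fix

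*SAP*

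**What the plan says.** SAP 5.5.1 (Serum and CSF PK Concentration Profile) sets the visits: "CSF to serum concentration ratio will be computed using pre-infusion concentrations at week 12, 48, 76, 128, 176, and 224". Individual ratios and descriptive statistics, including arithmetic mean, geometric mean and median, are given by dose. The BLQ rule has no conditions: "Any BLQ value will be excluded from CSF to serum ratio calculation, and exclusions will be appropriately documented". The scatter plot of CSF against serum is also limited to pairs in which both values exceed the LLOQ.

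Other outputs in the same section follow other rules. For serum descriptive statistics, "all post first dose of study treatment BLQ values will be set to half the LLOQ value", and the concentration plots also use LLOQ/2. For CSF there is a display rule, "Mean CSF concentrations that are BLQ will be presented as BLQ, and the SD and %CV will be reported as not applicable", but no rule for an individual BLQ value that enters a CSF mean. Listings keep the information: "Individual serum and CSF concentrations will be listed for BIIB092", with BLQ marked.

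SAP 3.1 adds an entry condition: "The CSF PK evaluable set is defined as subjects in the FAS who had at least one measurable post-baseline BIIB092 concentration in CSF". On CSF exposure, Protocol 4.5.1 reports from the two earlier studies that "the mean concentrations of BIIB092 in CSF increased in a generally dose-proportional manner". SAP 5.5 analyses the two low-dose regimens separately. No sensitivity analysis of the ratio is planned.

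**The concern.** A CSF value is BLQ because it is low. If its paired serum value is quantifiable, removing the pair cuts off part of the lower tail of the ratio and leaves the upper tail intact. If CSF levels scale with dose, the cut falls unevenly: 125 mg and 2000 mg on the same 4-week schedule differ 16-fold, so BLQ values should gather in the low-dose regimens. A table by dose could then show a falling ratio with rising dose where the true ratio is flat.

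Documenting the exclusions does not change the tabulated means and medians, and the scatter plot applies the same cut. At stake is the reading of one exploratory PK table in a study that also aims to inform dose selection.

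**Working it through.** The documents give no LLOQ, BLQ fraction, CSF level or variance for this trial, so there is no figure in the plan to reproduce. What follows is an illustration under stated assumptions.

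**Model.** ln C = ln S + ln R, where C is CSF, S is serum and R is the ratio. S and R are independent lognormals, and serum is always quantifiable.
- CSF CV: 40%, 60%, 80% (assumed). The log-SD is sC = √ln(1 + CV²) = 0.385, 0.555, 0.703.
- Share f of log-CSF variance that comes from serum: 0, 0.5, 0.75 (assumed).
- BLQ fraction q, with a = Φ⁻¹(q).

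**Mean ratio after exclusion, relative to true:** Φ((1 − f)·sC − a) / (1 − q).

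Example with CV 60%, f = 0.5, q = 0.3: Φ(0.277 + 0.524) / 0.7 = 0.789 / 0.7 = 1.13.

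Each cell gives the range over CV 40% to 80%:

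| Share of variance from serum | 10% BLQ | 30% BLQ | 50% BLQ |
|---|---|---|---|
| 0 | 1.06-1.08 | 1.17-1.27 | 1.30-1.52 |
| 0.5 | 1.03-1.05 | 1.09-1.16 | 1.15-1.27 |
| 0.75 | 1.02-1.03 | 1.05-1.08 | 1.08-1.14 |

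Over the whole grid the inflation is 2-8%, 5-27% and 8-52%. The top row, with serum constant, is the upper extreme. The geometric mean is inflated by exp[(1 − f)·sC·φ(a)/(1 − q)], which is larger. With CV 60%, f = 0 and 50% BLQ it is exp(0.555 × 0.399 / 0.5) = 1.56, against 1.42 for the arithmetic mean.

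**Spread over doses.** With dose-proportional CSF and equal log-SD, the BLQ fraction at 2000 mg is Φ(a − ln 16 / sC). Take 50% BLQ at 125 mg and the widest log-SD: Φ(−2.773 / 0.703) = Φ(−3.94), about 0.004%. At 600 mg it is Φ(−ln 4.8 / 0.703) = Φ(−2.23), about 1.3%. Any bias therefore sits almost wholly in the low-dose regimens.

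**The 12-week regimen.** Assume that active 375 mg infusions fall every 12 weeks from Day 1 and again from Week 80. Then five of the six ratio visits (Weeks 12, 48, 128, 176 and 224) are 12-week troughs. Week 76 falls 4 weeks after an active dose.

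**Who remains after exclusion.** The share of retained CSF values below the group's true median is (0.5 − q)/(1 − q): 44% at 10% BLQ, 29% at 30%, and none at 50%.

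**LLOQ/2 instead of exclusion** (simulation, same grid). The mean ratio is 0.97-0.99 of true at 10% BLQ, 0.90-0.97 at 30% and 0.86-0.97 at 50%. With 70% BLQ included, the range is 0.84-1.06. Up to about 50% BLQ the two rules err in opposite directions and bracket the truth.

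**The case against.** The strongest reply is that the bias may be negligible. If few low-dose CSF samples are BLQ, the ratio shifts by a few percent at most. The SAP's display rule for BLQ means is a formatting provision and does not predict that on-treatment low-dose means will be BLQ. This stands, and it is why the size can only be given as a range.

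A reader might infer that only participants with high CSF levels stay in the low-dose summaries. The documents do not support that. Exclusion is by sample and visit, and the statement would need about half or more of the samples to be BLQ.

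A reader might also infer that brain exposure is overstated. What can be overstated is the ratio. CSF concentrations are summarised separately by visit and dose group, and the SAP gives the ratio no stated role in dose selection.

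Nor is the direction fixed by the text alone. The rule also removes pairs in which only serum is BLQ, and those ratios would be high.

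The different rule for serum is not an error in itself. LLOQ/2 there serves serum summaries and plots, and a ratio can reasonably need its own rule. Finally, a reader could count BLQ values from the listings and the reported N. That makes the problem detectable but leaves the summary statistics as they are.

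**Conclusion.** The point holds in a limited form. Where CSF is the BLQ component, exclusion biases the by-dose ratio upward, and dose-proportionality places that bias chiefly at 125 mg every 4 weeks and at the 12-week troughs of 375 mg every 12 weeks. A flat ratio could therefore appear to fall with dose. The ranges above rest on lognormal data, independent serum and ratio, quantifiable serum, and assumed CVs and BLQ fractions. They show what is possible and do not estimate what will happen in this trial. The consequence is confined to an exploratory, descriptive PK output.

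**What to change.** Amend SAP 5.5.1 as follows.
- Keep the exclusion-based ratio as planned.
- Beside it, report the median and geometric mean ratio with CSF BLQ set to LLOQ/2 for all pairs with quantifiable serum, or give a censored-data (maximum likelihood) estimate. Exclude only serum-BLQ pairs from this second summary.
- Show n (%) CSF BLQ and n (%) serum BLQ by dose and visit. Count over everyone on BIIB092 who gave the sample, because the CSF PK evaluable set already leaves out participants who were always BLQ.
- State that a dose trend in the ratio will not be interpreted unless both summaries agree.

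LLOQ/2 should not replace exclusion outright. It is usually biased downward (mean about 0.84-1.06 of true over the settings above, up to 70% BLQ), and once half or more of the CSF values are BLQ its median rests largely on substituted values. Ranking BLQ ratios lowest and reporting that median is no safer: with half the variance from serum it is 4-7% too low at 30% BLQ and 15-25% too low at 45%.

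The cost is a short change to the SAP text and one more exploratory table. No new data are needed.
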